16.7.5. TREATMENT EMERGENT MANIA

Treatment-emergent mania is observed as either of the following:

- A YMRS total score ≥ 16 at 2 or more consecutive assessments.
- Treatment emergent adverse events related to mania symptoms, as assessed by a medical reviewer.

Number and percentage of patients with treatment emergent mania will be summarized by treatment group. Additionally, a logistic regression analysis will be performed with effects for treatment group, pooled center, and baseline YMRS total score. Contrasts will be evaluated for each SM-13496 treatment group compared to placebo. Odds Ratios, 95% CIs and Wald chi-square p-values will be presented for each contrast.

If the model fails to converge, the model will be attempted replacing pooled center with country. If model still does not converge, use geographic region (Asia, Non-Asia). Japan, Malaysia, Philippines and Taiwan are classified as belonging to Asia while Ukraine, Russia, Lithuania and Slovakia are classified as Non-Asian countries. Only n and percent will be presented in cases where the number of subjects meeting the above composite variable criteria is too small for an analysis to be performed.

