7.2. MULTICENTER STUDIES

This study will be conducted by multiple investigators at multiple centers internationally.

All centers with eleven or fewer randomized patients will be pooled by size within country or geographic region. No pooled center will contain more than 25 randomized patients. If the pooling cannot be performed within country, other centers in the same geographic region will be considered. The list of pooled centers for the present study based on the pooling strategy previously described is provided in Table B.

Table B: Pooled Sites

Document:	K:\DSP\SM-13496\KVA95374\Biostatistics\Documentation\SAP		
Author:	[REDACTED]	Version Number:	1.0
		Version Date:	30MAR2017

Template No: CS_TP_BS016 – Revision 3
Effective Date: 01May2012

Reference: CS_WI_BS005

Copyright © 2012 [REDACTED] All rights reserved. [REDACTED]
The contents of this document are confidential and proprietary to [REDACTED]. Unauthorized use, disclosure or reproduction is strictly prohibited.

Pooled Center ID	Center ID (Number of Subjects)	Country	Number of Subjects
901		JPN	21
902		JPN	21
903		JPN	13
904		JPN	23
905		JPN	22
906		JPN	22
907		JPN	24
908		JPN	17
909		JPN	16
910		LTU	22
		RUS	
911		MYS	19
912		PHL	24
		TWN	
913		RUS	22
914		RUS	24
915		RUS	17
916		RUS	24
917		RUS	18
918		RUS	13
919		RUS	15
920		SVK	16
921		UKR	19
922		UKR	17
923		UKR	17
924		UKR	15
925		UKR	15
926		UKR	14
927		UKR	13
928		UKR	21

A term for treatment by pooled center interaction will not be included in the primary analysis model, however, a sensitivity analysis, based on the primary model but including a term for treatment by pooled center interaction, will be performed.

Document: K:\DSP\SM-13496\KVA95374\Biostatistics\Documentation\SAP
 Author: [REDACTED] Version Number: 1.0
 Version Date: 30MAR2017

Template No: CS_TP_BS016 – Revision 3 Reference: CS_WI_BS005
 Effective Date: 01May2012

Copyright © 2012 [REDACTED] All rights reserved. [REDACTED] Unauthorized use, disclosure or reproduction is strictly prohibited.

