A composite measure of suicidality measures the presence of any suicidal ideation or behavior. The number and percentage of subjects with suicidality as measured by the C-SSRS will be summarized and compared among the SM-13496 treatment groups versus placebo using Fisher's exact test, where suicidality is defined as having at least one occurrence of suicidal ideation or at least one occurrence of suicidal behavior. The baseline suicidality indicator will be set to 1 if the subject exhibits suicidality during the two weeks prior to the baseline visit, 0 if the subject does not exhibit suicidality during the two weeks prior to the baseline visit, and missing otherwise. The post-baseline suicidality indicator is similarly defined for each post-baseline weekly visit. This analysis will be performed at Week 6, LOCF endpoint, and overall (based on all post-baseline visits up to and including LOCF endpoint) by treatment group and combined SM-13496 group.

An overall summary of post-baseline data across all visits up to and including LOCF endpoint will include the frequency and percentage of the following by treatment group and for the combined SM-13496 group:

- At least one suicidal ideation post-baseline
- No suicidal ideation post-baseline
- Emergence of suicidal ideation (no suicidal ideation at baseline, and any type of suicidal ideation post-baseline)
- Emergence of serious suicidal ideation (no suicidal ideation at baseline, and any serious suicidal ideation [ideation score of 4 or 5] post-baseline)
- Most severe type of ideation post-baseline
- Worsening of suicidal ideation (most severe suicidal ideation post-baseline was more severe than it was at baseline)
- At least one suicidal behavior post-baseline
- No suicidal behavior post-baseline
- Emergence of suicidal behavior (no suicidal behavior at baseline, and any type of suicidal behavior post-baseline)
- At least one actual attempt post-baseline
- At least one interrupted attempt post-baseline
- At least one aborted attempt post-baseline
- At least one preparatory act or behaviors post-baseline
- At least one instance of suicidality [any ideation or behavior] post-baseline
- No suicidality post-baseline

Document: K:\DSP\SM-13496\KVA95374\Biostatistics\Documentation\SAP

Author: [REDACTED]

Version Number:

1.0

Version Date:

30MAR2017

Template No: CS_TP_BS016 -- Revision 3

Reference: CS_WI_BS005

Effective Date: 01May2012

Copyright © 2012 [REDACTED] All rights reserved.

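### The planned logistic comparison of treatment-emergent mania gives no valid test when the placebo arm has no cases, and its convergence trigger is ambiguous when centers have none

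*SAP*

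**What the plan says.** SAP 16.7.5 counts a patient as having treatment-emergent mania if the YMRS total is 16 or more at two or more consecutive assessments, or if there is a mania-related treatment-emergent adverse event. Number and percentage are summarized by arm. In addition, "a logistic regression analysis will be performed with effects for treatment group, pooled center, and baseline YMRS total score", and "Odds Ratios, 95% CIs and Wald chi-square p-values will be presented for each contrast", each SM-13496 group against placebo.

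The sequence for sparse data is fixed in advance. "If the model fails to converge, the model will be attempted replacing pooled center with country"; if that also fails, a two-level region term (Asia or Non-Asia) is used. Finally, "Only n and percent will be presented in cases where the number of subjects meeting the above composite variable criteria is too small". No threshold is given for too small, and no exact or penalized method is named.

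SAP 7.2 defines the center term: "No pooled center will contain more than 25 randomized patients", and "The list of pooled centers for the present study based on the pooling strategy previously described is provided in Table B". The table runs from 901 to 928.

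Two other places matter. SAP 16.7.4 compares suicidality with placebo by Fisher's "exact test, where suicidality is defined as having at least one occurrence of suicidal ideation" or behavior. Protocol 9.7.4 plans only number and percentage for mania, so the logistic model is an SAP addition.

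**The concern.** A logistic model with treatment (3 levels), pooled center (28 levels) and baseline YMRS has 1 + 2 + 27 + 1 = 31 parameters. Entry requires a YMRS of 12 or less, so few patients may reach the event definition within six weeks. A center without a case has no finite coefficient; an arm without a case has no finite odds ratio. The fallbacks change only the site term, so they can address the first problem but not the second.

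Protocol 3.4.3 calls manic switching an important concern and names this measure for assessing it. With no cases on placebo and several on an active dose, the planned comparison would give either no test or a p-value that looks reassuring.

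**Working it through.** **Inputs.** From Table B: 28 pooled centers of 13 to 24 patients, summing to 524. From Protocol 4.2: 1:1:1 allocation, hence about 524/3 ≈ 175 per arm. From SAP 6.6: two-sided 5%. Mania rates are my assumption, since neither document gives one. The plan has no power figure for mania to reproduce; its only one (161 per group, 80%) concerns the MADRS.

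**Step 1: centers without cases.** With a common rate p, a center of size n has no case with probability (1−p)^n. The expected number of empty centers is Σ(1−p)^n, and the chance that none is empty is Π[1−(1−p)^n].

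| Assumed rate | Expected cases (524p) | Expected empty centers of 28 | Chance none is empty |
|---|---|---|---|
| 1% | 5.2 | 23.2 | below 1 in a million |
| 2% | 10.5 | 19.2 | below 1 in a million |
| 3% | 15.7 | 15.9 | below 1 in a million |
| 5% | 26.2 | 10.9 | below 1 in a million |
| 10% | 52.4 | 4.2 | 1% |

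So the center model practically never has a full maximum-likelihood solution at 1% to 5%.

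**Step 2: does that destroy the treatment contrast?** Not if every arm has cases. In five simulated trials with 14 to 17 empty centers, the fit on all patients and the fit without the empty centers gave the same treatment log odds ratios to within 0.001. The numerical routine reported convergence, but the estimate rested on only 209 to 267 of 524 patients.

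**Step 3: the fallback models.** Share of 1,000 simulated trials with an empty country (or region) or an empty arm, at 1%, 2%, 3% and 5%, treating each mixed-country row of Table B as one country level:
- country model: 100%, 99.5%, 95%, 83%
- region model: 47%, 10%, 2%, 0.1%

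**Step 4: a placebo arm without cases.** The probability is (1−p)^175:
- 0.5%: 0.995^175 = 0.416
- 1%: 0.99^175 = 0.172
- 2%: 0.98^175 = 0.029

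Both active-versus-placebo odds ratios are then infinite under center, country or region. With six cases in each active arm and none on placebo, a Newton-Raphson fit gave a Wald p of 0.67 to 0.70 after 10 iterations. Allowed 25, it gave 0.999, and the routine then declared convergence, so the fallback would not even be triggered.

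**Step 5: the exact test on the same kind of data.** For 0/175 versus 6/175, the chance that all six cases fall in one given arm is (175·174·173·172·171·170)/(350·349·348·347·346·345) = 0.01496. Doubled, p = 0.030. For 0 versus 5, p = 0.061; for 0 versus 7, p = 0.015.

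**Step 6: sensitivity.** I simulated 175 per arm, 45% in one region, both active arms at the higher rate, and the region model with Wald test, counting a separated fit as no test. The ranges are over repeated runs.

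| Placebo vs active rate | Region model, Wald | Fisher |
|---|---|---|
| 0.5% vs 3% | 6–7% | 24–26% |
| 1% vs 3% | 6–7% | 12–14% |
| 1% vs 4% | 19–21% | 30–32% |
| 2% vs 6% | 38–41% | 36–37% |
| 3% vs 8% | 48–52% | 43–46% |

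With equal rates of 1% to 2%, both tests reject in at most 2% of trials, so Fisher's gain in the upper rows does not come from inflated error.

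**The case against.** The SAP foresees sparse events and fixes the order of models in advance, so a choice by convergence is not a choice by the treatment result. The region model is usable in about 90% of simulated trials at 2% and 98% at 3%. Counts and percentages by arm are always shown, so 0 versus 6 would be visible without a p-value. Safety data are otherwise descriptive by default, and this comparison is unpowered and has no bearing on the primary analysis. Fisher's test is itself weak here (7 versus 1 of 175 gives p = 0.067) and ignores baseline YMRS, a plausible predictor. All of this stands, and it limits the point.

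A reader might infer three stronger things. One is that the center model cannot be fitted, so that the comparison always fails; Step 2 shows that the treatment contrasts survive empty centers when every arm has cases. Another is that the plan is less sensitive throughout; the last two rows of Step 6 show the region model doing as well or slightly better. The third is that the SAP treats suicidality as an equally rare event; it states no rate for it, so 16.7.4 shows only that an exact test is already in the plan.

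What the objection does not answer is the zero-case placebo arm. There the fixed sequence ends without a valid comparison, and the triggers (fails to converge, too small) do not say clearly which output will be reported.

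**Conclusion.** The point holds in a limited form. Where placebo has no case, no model in the sequence can estimate either contrast, and the plan reports counts alone or an uninformative Wald p near 1. This arises in about 42% of trials at a placebo rate of 0.5%, 17% at 1% and 3% at 2%. Among the scenarios tried, the loss of sensitivity appears only at placebo rates of about 1% or less, and is largest at 0.5% versus 3% (about 7% against 25%). Separately, empty centers are near certain at 1% to 5%, which makes the convergence trigger ambiguous and can leave the odds ratio resting on about half of the patients or fewer.

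These figures rest on assumed event rates that the documents neither support nor exclude, on one common rate across centers in Steps 1 and 3, and on the region model being the one reported in Step 6. The Wald values come from a general fitting routine, not from SAS. The issue is worth correcting because the outcome is a named safety concern and the remedy is small; primary efficacy is unaffected.

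**What to change.** In SAP 16.7.5, before unblinding, state that each SM-13496 group will be compared with placebo by Fisher's exact test with an exact confidence interval for the odds ratio or risk difference, following the test used for suicidality in 16.7.4. Either make this the main comparison or, at the least, require it whenever an arm has no cases or the fitted model shows separation. Define separation as the trigger, in place of reliance on the convergence message. If an adjusted estimate is wanted, use Firth-penalized logistic regression with region and baseline YMRS only.

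The cost is a few sentences and a few lines of code. The promise in Protocol 9.7.4 (number and percentage) is still met. The downside is that the exact test is not adjusted for center or baseline YMRS and, if it fully replaces the model, gives up a little sensitivity at higher event rates.

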16.8. PHARMACOKINETIC DATA

Samples for pharmacokinetic analysis are drawn at Week 3, Week 4 and Week 6/ Early Term. The data will be summarized, separated by timepoint and SM-13496 dose at time of sample collection.

Samples for pharmacokinetic analysis are drawn at Week 3, Week 4 and Week 6/ Early Term. For purposes of analysis, windows will be used based on scheduled visit and collection timepoint to select samples for summarization (see Table 12). All samples collected within these windows will subsequently be summarized. Samples collected outside the specified windows will be included only in a data listing. Samples collected from early terminated subjects should not be included in summaries and figures.

For blood samples, time in hours since last dose will be summarized by most recent assigned dose level and country (overall and each country) to assess whether samples were collected according to protocol-defined intervals. For inclusion at a given visit and collection timepoint, subjects will be required to have at least 5 days of exposure at the assigned dose level prior to sample collection.

Blood concentrations of SM-13496 and selected quantifiable metabolites (which may include, but are not limited to, ID-11614, ID-14283, and ID-14326) will be summarized at each visit by most recent assigned dose level. For inclusion at a given visit and collection timepoint, subjects will be required to have at least 5 days of exposure at the assigned dose level prior to sample collection. SM-13496 treatment group (actual dose) mean pharmacokinetic sample concentrations and respective standard deviations will be plotted by visit and dose and country (overall and each country) using box plot style in the Safety population. Concentrations will also be plotted by visit, dose and country using a box plot style based on the Safety population.

Document:	K:\DSP\SM-13496\KVA95374\Biostatistics\Documentation\SAP		
Author:	[REDACTED]	Version Number:	1.0
		Version Date:	30MAR2017

Template No: CS_TP_BS016 – Revision 3
Effective Date: 01May2012

Reference: CS_WI_BS005

Copyright © 2012 [REDACTED] All rights reserved.
The contents of this document are confidential and proprietary to [REDACTED]. Unauthorized use, disclosure or reproduction is strictly prohibited.

Table 12 - Pharmacokinetic Sample Windows to Select Data for Summarization

Visit	Sample Windows
Week 3	Within 13-15 hours post-dose
Week 4	Within 13-15 hours post-dose
Week 6	Within 13-15 hours post-dose

17. DATA NOT SUMMARIZED OR PRESENTED

The other variables and/or domains not summarized or presented are:

- Comments
- MINI screening questionnaire

These domains and/or variables will not be summarized or presented, but will be available in the clinical study database, SDTM and/or ADaM datasets.

Document: K:\DSP\SM-13496\KVA95374\Biostatistics\Documentation\SAP

Author: [REDACTED]

Version Number:

1.0

Version Date:

30MAR2017

Template No: CS_TP_BS016 – Revision 3

Reference: CS_WJ_BS005

Effective Date: 01May2012

Copyright © 2012 [REDACTED] All rights reserved.

The contents of this document are confidential and proprietary to [REDACTED]. Unauthorized use, disclosure or reproduction is strictly prohibited.

APPENDIX 1. PROGRAMMING CONVENTIONS FOR OUTPUTS

OUTPUT CONVENTIONS

Outputs will be presented according to the following conventions, which follow Sumitomo output conventions but use information from previous SM-13496 study layout:

1. ABBREVIATIONS

- ASCII American standard code for information interchange file format
- CGM Computer graphics metafile
- ODS Output Delivery System
- RTF Rich text file format

2. INTRODUCTION

This document applies to standards used for outputting tables, listings and figures. It is intended to provide specifications to guide the statistician or statistical programmer in setting up specifications for programming tables, listings and figures. These standards should be used in the absence of customer specific standards.

3. OUTPUT FILE NAMING CONVENTIONS

File names should only consist of lowercase letters, digits (0 to 9) and dashes. A period should only be used to indicate a separator between the file name and the extension. No spaces, other special characters or punctuation marks are permitted. As dashes are not permitted in SAS program names, they will be replaced by underscores.

Output files should be in RTF format.

The program, program log and output file name should reflect the type and number of the statistical output. If this is not possible, then the output name should be at least as descriptive as possible. A prefix can be used to distinguish between a Table, Listing and Figure document ('t' for table, 'l' for listing and 'f' for figure). If there is only 1 digit in the number of the table, listing or figure in the place where 2 digits are possible, a leading zero should be added in the file name to make sorting consistent with the sequence (eg t14-3-01-1.RTF)

4. PAPER SIZE, ORIENTATION AND MARGINS

- The size of paper will be A4.
- The page orientation should preferably be landscape, but portrait is also permitted.

Document: K:\DSP\SM-13496\KVA95374\Biostatistics\Documentation\SAP
Author: [REDACTED] Version Number: 1.0
Version Date: 30MAR2017

Template No: CS_TP_BS016 – Revision 3
Effective Date: 01May2012

Reference: CS_WI_BS005

Copyright © 2012 [REDACTED] All rights reserved.
The contents of this document are confidential and proprietary to [REDACTED]. Unauthorized use, disclosure or reproduction is strictly prohibited.

- Margins should provide at least 3 centimeters of white space all around the page, regardless of the paper size.
- The number of columns per page (linesize) should be 132 for A4.
- The number of rows per page (pagesize) should be 46 for A4.

5. FONTS

The font type Times New Roman should be used as a default for tables and listings, with a font size of 8. The font color should be black. No bolding, underlining italics or subscripting should be permitted. Try to avoid using super-scripts, unless absolutely necessary. Single spacing should be used for all text.

Figures should have a default font of "Times Roman", "Helvetica", or "Courier New".

This can be achieved by using the following options in SAS:

```
goptions  
gunit = pct  
cback = white  
colors = (black)  
hby = 2.4  
ftext = "TimesRoman"  
htext = 2.5  
device = cgmof97i  
gaccess = gsasfile;  
filename gsasfile "....cgm";
```

6. HEADER INFORMATION

Headers should be defined as follows:

- The header should be placed at the top of the page (same place on each page) regardless of the size or orientation of the table or listing
- The customer name and protocol number should appear in row 1, left-aligned
- The output identification number should appear in row 2, centered
- The output title should start in row 3, centered
- The output population should appear in row 4, centered. The population should be spelled out in full, e.g. Intention-to-Treat in preference to ITT.
- Row 5 should be a continuous row of underscores ('_') (the number of underscores should equal the linesize)
- Row 6 should be a blank line
- Mixed case should be used for titles
- The output titles should be designed so that they are arranged consistently through all outputs. For example, content (eg Vital Signs) followed by metric (eg Change from Baseline) e.g. Vital Signs – Change from Baseline.

Document:	K:\DSP\SM-13496\KVA95374\Biostatistics\Documentation\SAP	Version Number:	1.0
Author:	[REDACTED]	Version Date:	30MAR2017

Template No: CS_TP_BS016 – Revision 3

Reference: CS_WI_BS005

Effective Date: 01May2012

Copyright © 2012 [REDACTED] All rights reserved

The contents of this document are confidential and proprietary to [REDACTED]. Unauthorized use, disclosure or reproduction is strictly prohibited.

- Titles should not contain quotation marks or footnote references
- The column headings should be underlined with a row of underscores ('_')
- Column headings spanning more than one column should be underlined and have underscores on either side of the title and should be centered
- Column headings containing numbers should be centered
- Column headings should be in proper case
- In general, the population count should appear in the column header in the form "(N=XXX)"
- "Statistic" should be the column header over n, Mean, SE, n (%) etc.
- As a rule, all columns should have column headings.
- The header of the outputs will be in a non-selectable format for all pages after page one.

7. TABLE AND LISTING OUTPUT CONVENTIONS

General:

- The first row in the body of the table or listing should be blank
- The left hand column should start in column 1. No indenting or centering of the output should occur.
- Rounding should be done with the SAS function ROUND.
- Numbers in tables should be rounded, not truncated.
- Alphanumeric output should be left aligned.
- Numbers should be decimal point aligned.
- Whole numbers should be right aligned.
- Text values should be left aligned.
- The first letter of a text entry should be capitalized
- Listings of adverse events, concomitant medications, medical histories etc. should be sorted in chronological order, with earliest adverse event, medication or history coming first.
- Placebo should appear first in tables with treatments as columns
- In general, only present totals (across treatment groups) at baseline/randomization, and do not present them post randomization, unless the customer specifically requests it.

Document: K:\DSP\SM-13496\KVA95374\Biostatistics\Documentation\SAP

Author:

Version Number:

1.0

Version Date:

30MAR2017

Template No: CS_TP_BS016 – Revision 3

Reference: CS_WI_BS005

Effective Date: 01May2012

Copyright © 2012 [REDACTED]. All rights reserved.
The contents of this document are confidential and proprietary to [REDACTED].
reproduction is strictly prohibited.

Unauthorized use, disclosure or

- If possible, include 100% frequencies in the table shell, so that it is clear what the denominator is for percentage calculations.
- All listing outputs should be sorted (preferably by Treatment, Site Number and Subject Number).
- Exponentiation will be expressed using a double asterisk, i.e., mm³ will be written as mm**3.
- All variables that are output in the CRF (which have data present) should appear in the listings, along with all derived data appearing in the corresponding tables
- The width of the entire output should match the linesize

Univariate Statistics:

- Statistics should be presented in the same order across tables (i.e., n, Mean, SD, Median, Minimum, Maximum)
- Table statistics should line up under the N part of the (N=XXX) in the table header. All decimal points should line up. If the minimum and maximum are output on one line as Minimum, Maximum then the comma should line up with the decimal point. It is accepted that using the Times New Roman font there will be limitations to this, though it will be followed as far as is possible.
- If the original data has N decimal places, then the summary statistics should have the following decimal places:
 - Minimum and maximum: N
 - Mean, median and CV%: N + 1
 - SD: N + 2

Frequencies and percentages (n and %):

- Percent values should be reported inside parentheses, with one space between the count and the left parenthesis of the percentage. Parentheses should be justified to accept a maximum of 100.0 as a value and padded with blank space if the percent is less than 100.0. An example is given below:

77 (100.0%)

50 (64.9%)

0 (0.0%)

- Percentages will be reported to one decimal place, except percents <100.0% but >99.9% will be presented as '>99.9%' (e.g., 99.99% is presented as >99.9%); and percents < 0.1% will be presented as '<0.1%' (e.g., 0.08% is presented as <0.1%). Rounding will be applied after the <0.1% and >99.9% rule.

Eg (<0.1%)

Document: K:\DSP\SM-13496\KVA95374\Biostatistics\Documentation\SAP
Author: [REDACTED] Version Number: 1.0
Version Date: 30MAR2017

Template No: CS_TP_BS016 – Revision 3

Reference: CS_WI_BS005

Effective Date: 01May2012

Copyright © 2012 [REDACTED] All rights reserved. [REDACTED] Unauthorized use, disclosure or reproduction is strictly prohibited.

(6.8%)

(>99.9%)

- Percentages may be reported to 0 decimal places as appropriate (for example, where the denominator is relatively small).
- Where counts are zero, percentages will not appear in the output.

Confidence Intervals:

- As a rule confidence intervals are output to one place more than the raw data, and standard deviations and standard errors to two places more than the raw data
- Confidence intervals should be justified so that parentheses displayed on consecutive lines of a table "line up".
- Boundary values of confidence intervals should be separated by a comma.
- Boundary values should be padded as necessary to accept negative values and to allow alignment of the decimal place.
- An example is given below:

(-0.12, -0.10)

(9.54, 12.91)

P-values:

- P-values should be reported to three decimal places, except values <1.000 but >0.999 will be presented as '>0.999' (e.g., 0.9998 is presented as >0.999); and values <0.001 will be presented as '<0.001' (e.g., 0.0009 is presented as <0.001). Rounding will be applied after the <0.001 and >0.999 rule

Ratios:

- Ratios should be reported to one more decimal place than the original data.

Spacing:

- There must be a minimum of 1 blank space between columns (preferably 2)

Document: K:\DSP\SM-13496\KVA95374\Biostatistics\Documentation\SAP

Author: [REDACTED]

Version Number:

1.0

Version Date:

30MAR2017

Template No: CS_TP_BS016 – Revision 3

Reference: CS_WI_BS005

Effective Date: 01May2012

Copyright © 2012 [REDACTED] All rights reserved.

The contents of this document are confidential and proprietary to [REDACTED] reproduction is strictly prohibited.

Unauthorized use, disclosure or

Denominators:

- If a different count other than the population count is used for a denominator (within the table) to calculate percentages, there should be a row in the table that identifies that number "n".
- Alternatively, a footnote should be included in each table with percentages to indicate the denominator for percentages.

Missing values:

- A "0" should be used to indicate a zero frequency.
- A blank will be used to indicate missing data in an end-of-text table or subject listing.
- In the case that only a single value is used in the creation of summary statistics (i.e. n=1) then only n and the mean will be presented.

